7.6.2 Pembrolizumab Administration and Storage

Trial treatment should be administered on Day 1 of each cycle after all procedures/assessments have been completed as detailed on the Trial Flow Chart (Section 8.0). Trial treatment may be administered up to 3 days before or after the scheduled Day 1 of each cycle due to administrative reasons.

All trial treatments will be administered on an outpatient basis.

Pembrolizumab is supplied free of charge by Merck and Co.

Pembrolizumab 200 mg will be administered as a 30 minute IV infusion every 3 weeks. Sites should make every effort to target infusion timing to be as close to 30 minutes as possible. However, given the variability of infusion pumps from site to site, a window of -5 minutes and +10 minutes is permitted (i.e., infusion time is 30 minutes: -5 min/+10 min).

The Pharmacy Manual contains specific instructions for the preparation of the pembrolizumab infusion fluid and administration of infusion solution.

Pembrolizumab Solution for Infusion is a sterile, non-pyrogenic aqueous solution supplied in single-use Type I glass vial containing 100 mg/4 mL of pembrolizumab. The product is preservative-free, latex free solution which is essentially free of extraneous particulates.

Pembrolizumab (MK-3475) Solution for Infusion vials are filled to a target of 4.25mL (106.25mg) to ensure recovery of 4.0mL (100mg).

Pembrolizumab (MK-3475) Solution for Infusion, 100 mg/ 4 mL vial: pembrolizumab Solution for Infusion vials should be stored at refrigerated conditions 2 - 8 °C (36 - 46 °F) and protected from light. Do not shake and do not freeze. Vials should be stored in the original box to ensure the drug product is protected from light.

Pembrolizumab (MK-3475) infusion solutions should be prepared in **0.9% Sodium Chloride Injection, USP** (normal saline) or regional equivalent or 5% Dextrose Injection, USP (5% dextrose) or regional equivalent and the final concentration of pembrolizumab in the infusion solutions should be between 1 mg/mL and 10 mg/ml.

The infusion solution should be administered through an intravenous line containing a sterile, non-pyrogenic, low-protein binding, 0.2 micron to 5 micron in-line or add-on filter.

Pembrolizumab should not be mixed with other diluents.

From a microbiological point of view, diluted solution should be used as soon as possible after preparation.

Pembrolizumab solutions (which contain no preservative) may be stored at room temperature for a cumulative time of up to 6 hours. The 6-hour countdown begins when the vial is pierced and includes room temperature storage of admixture solutions in the IV bags and the duration of infusion. (Please note this 6-hour timeframe is to provide a microbial control strategy. The microbial clock only starts when the product stopper is pierced and not when the vial is removed from the refrigerator.)

In addition, IV bags may be stored under refrigeration at 2°C to 8°C (36 °F to 46 °F), total cumulative storage time at room temperature and refrigeration should not exceed 24 hours.

Temperature monitoring records are required when pembrolizumab admixture solution is refrigerated during storage or transfer. Only a period with recorded 2-8 °C can be accounted

for refrigerated time. Time when temperature is above 8 °C and below 25°C should be deducted from a 6-hour room temperature storage time bucket.

If refrigerated, allow the IV bags to come to room temperature prior to use.

Parenteral drug products should be inspected visually for particulate matter and discoloration prior to administration. Discard the drug product vial if visible particles are observed. In addition, the following precautions should be observed:

- **Do not use pembrolizumab if discoloration is observed.**
- **Do not shake or freeze the vial(s).**
- **Do not administer the product as an intravenous (iv) push or bolus.**
- **Do not combine, dilute or administer it as an infusion with other medicinal products.**

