4.5.1 Pharmacology

Vorinostat, the drug form of the compound suberoylanilide hydroxamic acid (SAHA, or MK-0683), is a novel agent that inhibits the enzymatic activity of histone deacetylases (HDACs). Vorinostat is a potent inhibitor of HDAC activity and binds directly to the catalytic pocket of Class I and II HDAC enzymes. Vorinostat inhibits the enzymatic activity of both Class I (HDAC1, 2 and 3) and Class II (HDAC6) HDACs at low nanomolar concentrations (IC50<86 nM). The anti-neoplastic effect of vorinostat is attributed to the inhibition of HDAC activity and subsequent accumulation of acetylated proteins, including the core nucleosomal histones. This accumulation influences the regulation of gene expression. Exposure to vorinostat led to G1 or G2 phase cell-cycle arrest, apoptosis, or differentiation in cultured transformed cells. The growth inhibitory activity of vorinostat was demonstrated on the 60 cell line screen at National Cancer Institute (NCI), with IC50s ranging from approximately 38.6 nM to 6.2 μ M. Additionally, vorinostat demonstrated synergistic and additive activity in combination with other cancer therapies (including radiation, kinase inhibitors, cytotoxic agents, and differentiating agents) in a variety of cultured human transformed cell lines.

The pharmacokinetics and toxicokinetics of vorinostat have been evaluated in mice, rats, dogs and humans. Rapid oral absorption has been noted in all species studied. Vorinostat (0.5 to 50 μ g/mL) exhibited moderate reversible binding to plasma proteins. In human plasma, vorinostat appears to bind primarily to human serum albumin; however, some binding of vorinostat was also observed in solutions of human α 1-acid glycoprotein.

Vorinostat is excreted exclusively as metabolites, the majority of metabolites are derived from glucuronidation and hydrolysis with β -oxidation pathway metabolites accounting for the rest. As vorinostat is not eliminated via cytochrome P450 pathways, it is anticipated that vorinostat will not be subject to drug-drug interactions when co-administered with drugs that are known to be CYP inhibitors. Although vorinostat was not a potent reversible inhibitor of the cytochrome P450 isozymes (IC50 >75 μ M), gene expression studies detected some potential for suppression of CYP2C9 and CYP3A4 activities at \geq 10 μ M vorinostat however, these changes were observed at concentrations higher than the pharmacologically relevant serum concentration of 2 μ M (Cmax).

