4.5.2 Toxicology

The main toxicities observed in *in vivo* animal models were weight loss and inappetence, anemia (rats only at 3.6 times the equivalent 400 mg human dose), leukopenia (rats only at 1.3 times the equivalent 400 mg human dose), thrombocytopenia (male rats only, statistically significant change at 0.5 times the equivalent 400 mg human dose but within normal range at all doses), and gastrointestinal tract irritation (dogs only, at 8.5 times the equivalent 400 mg human dose). Although statistically significant and dose-dependent, many of the clinical pathology findings were within normal historical ranges indicating that they should not have major toxicological consequences. The toxicities appeared to be rapidly reversible within 12 to 14 days. There has been no evidence of cardiac toxicity based on electrocardiogram (ECG, dogs only), blood pressure (dogs only), heart rate (dogs only), creatinine kinase, organ weight, gross pathology, or histopathology assessments in studies up to one month duration. No serious, irreversible damage to any vital organ has been observed. Importantly, toxicities in rats and dogs were predictive of adverse effects in humans (thrombocytopenia, anaemia, nausea, diarrhea, fatigue). Toxicities present in animals would be manageable in the clinic, and the onset of serious toxicity is readily forecast by prodromal symptoms. The nonclinical toxicity profile of vorinostat is acceptable for an oncology drug.

Vorinostat was evaluated in a panel of genetic toxicity assays; *in vivo* and *in vitro* assays were found to be positive. Therefore, vorinostat should not be taken by pregnant women. Pregnancy should be avoided both in female subjects taking vorinostat, and in female partners of male subjects taking vorinostat for at least 30 days after last dose of vorinostat, as data are not yet available to establish the safety of vorinostat ingestion in male patients who impregnate their partners.

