4.5.5 Safety

The total daily doses studied ranges from 200 mg to 900 mg. The tolerability of oral vorinostat appears to be determined by total daily dose and the length of consecutive days of dosing. The maximum tolerated dose (MTD) for continuous daily dosing without a rest period is 400 mg daily or 200 mg BID. The MTD for intermittent dosing is 300 mg BID x 3 consecutive days per week, or 250 mg TID x 14 consecutive days followed by a 7-day rest. Dose-limiting toxicities (DLTs) of single agent vorinostat were mainly non-hematologic (anorexia, dehydration, diarrhea, and fatigue); hematologic toxicities are primarily anemia and thrombocytopenia, most of which were mild to moderate. The majority of these DLTs occurred within the first month on oral vorinostat. The DLTs were manageable because these toxicities resolved quickly after drug administration was interrupted. The optimal dose, dose frequency, and dose duration remain under active investigation.

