QTc prolongation has been observed in patients receiving vorinostat although no statistical correlation has been established between the use of vorinostat and QTc prolongation. If clinically indicated or outlined in the respective study, baseline and periodic ECGs should be performed during treatment. Vorinostat should be administered with particular caution in patients with congenital long QT-syndrome and patients taking anti-arrhythmic medicines or other medicinal products that lead to QT prolongation.

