7.1 Treatment Allocation

There will be no randomization or stratification as part of this study. All patients who consent to the study, meet eligibility criteria, and are registered on the trial will receive study treatment.

This is a phase I study, including a dose-escalation portion of the study with 2 dose levels and 2 possible de-escalation dose levels, for a total of 4 possible dose levels. The starting dose will

be 100mg of vorinostat twice a day (BID), and 200mg IV pembrolizumab. Subjects will receive oral vorinostat according to dose level schedule and dose. Pembrolizumab will be administered on day 1 of each cycle thereafter. Study therapy will be administered in 21-day cycles. The planned dose levels in the dose-escalation portion of the study are outlined in Table 3 below.

Once the RP2D has been determined, an expansion cohort of 40 patients will be enrolled and treated at the RP2D, to acquire additional safety and tolerability data about the combination.

Table 3. Phase I Dose Levels

Dose Level	Vorinostat	Pembrolizumab (day 1)
-2	100mg PO BID, d1-3, 8-10	200mg IV
-1	100mg PO BID, d1-3, 8-10, 15-17	200mg IV
1 (starting)	100mg PO BID, d1-5, 8-12	200mg IV
2	200mg PO BID, d1-5, 8-12	200mg IV

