8.0 TRIAL FLOW CHART (STUDY CALENDAR)

8.1 Study Flow Chart

Trial Period:	Screening Phase	Treatment Cycles ^a												End of Treatment	Post-Treatment	
		To be repeated beyond 8 cycles				8				Discon	Safety Follow-up	Follow Up Visits ^g	Survival Follow-Up			
Treatment Cycle/Title:		1	2	3	4	5	6	7	8				D 1		D 15	
		D 1	D 8	D 15	D 1	D 1	D 1	D 1	D 15				D 1		D 15	
Scheduling Window (Days):	-28 to D1	± 3	± 3	± 3	± 3	± 3	See b	± 3	± 3	± 3	± 3	See b	At time of Discon ^l	30 days post discon ^m	Every 12 weeks post discon [†]	
Administrative Procedures																
Informed Consent	X															
Inclusion/Exclusion Criteria	X															
Demographics and Medical History	X															
Prior and Concomitant Medication Review	X															
Post-study anticancer therapy status													X	X	X	
Survival Status		X		X	X	X		X	X	X	X		X	X	X	X
Clinical Procedures/Assessments																
Vorinostat administration		X		X	X	X		X	X	X	X					
Pembrolizumab administration		X		X	X	X		X	X	X	X					
Review Adverse Events		X	X		X	X	X	X	X	X	X		X	X		
Physical Examination	X	X	X		X	X	X	X	X	X	X		X	X		
Vital Signs, Weight, and oxygen saturation	X	X	X		X	X	X	X	X	X	X		X	X		
ECOG Performance Status	X	X	X		X	X	X	X	X	X	X		X	X		
Buccal swab		X														
Laboratory Procedures/Assessments: analysis performed by LOCAL laboratory																

CONFIDENTIAL

Page 77 of 152

Trial Period:	Screening Phase	Treatment Cycles ^a												End of Treatment	Post-Treatment		
		1			2		3		4		To be repeated beyond 8 cycles				Discon	Safety Follow-up	Follow Up Visits ^g
Treatment Cycle/Title:		D 1	D 8	D 15	D 1	D 1	D 1	D 15	D 1	D 1	D 1	D 1	D 15				
		± 3	± 3	± 3	± 3	± 3	± 3	See b	± 3	± 3	± 3	± 3	See b	At time of Discon ^l	30 days post discon ^m	Every 12 weeks post discon [†]	
Pregnancy Test - Urine or Serum β-HCG ⁿ	X ^{**}	X			X	X	X		X	X	X	X		X	X		
PT/INR and aPTT [*]	X																
CBC with Differential [*]	X	X	X	X	X	X			X	X	X	X		X	X		
Comprehensive Serum Chemistry Panel ^c *	X	X	X	X	X	X			X	X	X	X		X	X		
Urinalysis [*]	X																
T3, FT4 and TSH (thyroid panel)		X			X				X					X			
12-lead ECG	X	X			X	X	X		X					X			
Efficacy Measurements																	
PET-CT or CT N/C/A/P ^e	X							X				X	X ^k		X ^d		
Tumor Biopsies/Archival Tissue Collection/Correlative Studies Blood																	
Archival or Newly Obtained Tumor Tissue Collection	X												X ^f				
Bone Marrow Aspirate and Biopsy ^j	X ⁱ																
Correlative Studies Blood Collection		X		X				X ⁱ				X ^h					

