
* Should be performed within 14 days of treatment initiation. After Cycle 1, pre-dose laboratory procedures can be conducted up to 72 hours prior to dosing.

** Female subjects of childbearing potential should have a negative urine or serum pregnancy within 72 hours prior to receiving the first dose of study medication.

† Imaging time point will be every 12 weeks (\pm 7 days) during the first year, and every 18 weeks thereafter (\pm 7 days).

a Vorinostat and pembrolizumab will be administered according to dose level in the Phase I dose-escalation portion of study and at RP2D in the expansion cohort portion of study. Vorinostat will be administered according to dose level, pembrolizumab will be administered on day 1 of each cycle. Cycle length will be 21 days.

b Should be performed between Day 15 and Day 21 (-3 days).

c Albumin, alkaline phosphatase, total bilirubin, bicarbonate, BUN, calcium, chloride, creatinine, glucose, LDH (only for DLBCL and FL patients), potassium, total protein, SGOT [AST], SGPT [ALT], sodium, uric acid, phosphorus, magnesium and direct bilirubin (if total bilirubin is elevated above the upper limit of normal).

d After 1 year, the imaging time point will occur every 18 weeks (+/- 7 days).

e PET-CT or CT N/C/A/P will be performed on cycle 4 day 15-21 (-3 days), cycle 8 day 15-21 (- 3 days), and every 4 cycles thereafter on day 15-21 (-3 days). Note: if there is no evidence of neck involvement by lymphoma at baseline, CT of chest, abdomen and pelvis (C/A/P) can be performed instead of N/C/A/P at subsequent re-staging. See sections 9.2.6 and 10.1 for additional imaging details.

f Collection of tumor tissue (fresh or archival) from standard of care tumor biopsy performed at the time of lymphoma relapse/progression, unless the tumor is inaccessible or there is a safety concern.

g Study follow-up period for subjects who remain on study but discontinue study treatment for a reason other than PD will remain on study and continue onto the Study Follow-up Period, and scans should be performed every 12 weeks (and then every 18 weeks after the first year, see †) starting from last on-treatment scan.

h For participants who progress during this study: Efforts should be made to collect a blood sample (if not collected within the last 30 days) at a planned SOC visit or a protocol visit. It will not be a deviation if the SOC visit/protocol visit falls outside of the \pm 30 day window.

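### No scheduled ECG has to be taken under vorinostat exposure: cycle ECGs fall on Day 1, read as pre-dose, about 10 days after the last vorinostat dose at levels 1 and 2

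*Combined protocol and SAP*

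**What the plan says.** **Order on Day 1.** Section 7.6.2 states: "Trial treatment should be administered on Day 1 of each cycle after all procedures/assessments have been completed as detailed on the Trial Flow Chart". It allows Day 1 to move by up to 3 days either way.

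**ECG schedule.** Read by column position, the 12-lead ECG row of 8.1 is marked at screening, Day 1 of cycles 1 to 5, and discontinuation. Days 8 and 15 of cycle 1 are blank. The chart header indicates that the block repeats beyond cycle 8. Under footnote l the discontinuation assessments are due within 10 days of stopping, with no link to a dose.

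**Vorinostat days.** Table 3 in 7.1 gives level 1 as "100mg PO BID, d1-5, 8-12". Level 2 has the same days at 200 mg. Level -1 ends on Day 17 and level -2 on Day 10. Cycles last 21 days.

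**Order of the two drugs.** The procedure list in 9.5.3.2 has vorinostat given in clinic before pembrolizumab.

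**QTc.** Section 4.5.6 says: "QTc prolongation has been observed in patients receiving vorinostat although no statistical correlation has been established between the use of vorinostat and QTc prolongation". Exclusion criterion 15 in 5.1.3 sets a QTcF limit of 470 ms.

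**The concern.** Toxicity is the primary endpoint, and the plan treats QTc as relevant: it screens on QTcF and schedules serial ECGs. Yet none of those ECGs has to be taken near a dose of the agent for which the protocol lists QTc prolongation. The C1D1 ECG comes before any drug. The later ones come at the end of a treatment-free stretch.

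If a QTc effect is short-lived, normal cycle ECGs say little about it. Asymptomatic prolongation during dosing days could then go unseen, and a safety report that lists normal ECGs without their timing could reassure more than the data allow.

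**Working it through.** The plan states no figure on this point, so there is none to reproduce. The check is day arithmetic, a sensitivity calculation, and a count of the patients a change could reach.

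**1. Gap from last vorinostat dose to next Day 1.** With 21-day cycles the next Day 1 is Day 22, so gap = 22 − last vorinostat day. The ±3-day window in 7.6.2 gives the range.

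| Level | Last dose day | Gap (days) | With ±3 days |
|---|---|---|---|
| 1 and 2 | 12 | 22 − 12 = 10 | 7 to 13 |
| -1 | 17 | 22 − 17 = 5 | 2 to 8 |
| -2 | 10 | 22 − 10 = 12 | 9 to 15 |

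The level -1 and -2 rows also apply to patients reduced to those levels under Table 6. Of the four marked cycle ECGs after first exposure (C2D1 to C5D1), none is required near a dose. Any repeat of the block in later cycles has the same Day 1 timing.

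**2. How much of an effect would remain.** The documents give no vorinostat half-life, QTc time course or effect size. The nearest statements are not about QTc. On single-agent dose-limiting toxicities, 4.5.5 says "these toxicities resolved quickly after drug administration was interrupted". On animal findings, 4.5.2 says "The toxicities appeared to be rapidly reversible within 12 to 14 days". The half-lives below are therefore assumptions. Share remaining = 2^(−gap / half-life of the effect).

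| Gap (days) | 1-day half-life | 3-day | 7-day | 14-day |
|---|---|---|---|---|
| 10 (levels 1, 2) | 0.1% | 10% | 37% | 61% |
| 5 (level -1) | 3% | 31% | 61% | 78% |
| 12 (level -2) | <0.1% | 6% | 30% | 55% |

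A fast-fading effect would be essentially gone at the cycle ECG. One that lasts about two weeks would mostly still show.

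**3. Who can still benefit.** Section 4.6.4 reports 42 patients enrolled and 10 more planned: 52 − 42 = 10. The cap in 11.3 gives 60 − 42 = 18. Both are upper figures if some of these patients have already started. Under 7.1.2, four levels of at most 6 hold 4 × 6 = 24 evaluable patients, well below 42, so dose finding is past.

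**4. What those patients could show.** With no events, the exact two-sided 95% upper limit is 1 − 0.025^(1/10) = 30.8% for 10 patients and 1 − 0.025^(1/18) = 18.5% for 18. If the true frequency were 10%, the chance of at least one event is 1 − 0.9^10 = 65% or 1 − 0.9^18 = 85%.

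**The case against.** **The plan meets the only ECG standard it cites.** Section 4.5.6 asks for baseline and periodic ECGs where indicated or where the study provides for them, and sets no timing relative to a dose. QTc is not an endpoint or a planned analysis. This stands, and it is why the point is minor.

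**No QTc effect is established.** Section 4.5.6 says so, and 4.5.2 reports no ECG evidence of cardiac toxicity in dogs. The share remaining at levels 1 and 2 runs from 0.1% to 61% across the assumed half-lives, so the documents do not settle whether the ECGs miss anything. This also stands. It does not favour the present timing, since an ECG shortly after a dose is at least as informative about vorinostat for any plausible fade rate.

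**The pre-dose reading is inferred.** The sentence in 7.6.2 sits in the pembrolizumab section, and 9.5.3.2 gives vorinostat first. An ECG between the two drugs may therefore be permitted, but nothing requires one.

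**The flow chart was read from a PDF.** Some rows are visibly displaced: the correlative-blood row does not match 9.4.1. The ECG row agrees with the pregnancy-test row through C5D1, which supports the Day 1 reading, but the original page should be checked.

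**Unscheduled ECGs are allowed** (9.0). These depend on clinical suspicion, so the gap concerns asymptomatic events.

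**Conclusion.** The point holds as a minor safety-monitoring improvement. No scheduled ECG is required under vorinostat exposure, and the cycle ECGs come about 10 days after the last dose at levels 1 and 2 (5 at level -1, 12 at level -2). This rests on the column reading of 8.1 and the natural reading of 7.6.2. That prolongation could be missed rests further on the assumption that a QTc effect fades within days.

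A reader might infer three stronger things that the documents do not support:

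- **That QTc events or dose-limiting toxicities were missed in dose finding.** Nothing shows that any occurred.
- **That all ECGs so far were taken off drug.** Post-vorinostat ECGs on Day 1, unscheduled ECGs and discontinuation ECGs near a dose were all possible.
- **That the cycle ECGs cannot show a vorinostat effect.** A slow-fading one would largely remain.

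With about 10 patients left to reach, and at most 18, the change gives a signal check and not a rate estimate.

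**What to change.** **Flow chart.** Add a footnote to the ECG row of 8.1: the existing C2D1 ECG is recorded after the in-clinic vorinostat dose and before the pembrolizumab infusion, in the order of 9.5.3.2, with dose time and ECG time noted. Exempt this one ECG from the assessments-before-treatment sentence in 7.6.2. The sponsor should set the interval after the dose from the Investigator's Brochure, because 4.5.1 says only "Rapid oral absorption has been noted in all species studied" and gives no time to peak. If vorinostat is on hold that day, mark the ECG as off drug. Keep the other cycle ECGs pre-dose, so that a slow-fading effect can still be seen. By column position, the "Comprehensive Serum Chemistry Panel" is already marked at C2D1, and footnote c includes "potassium, total protein, SGOT [AST], SGPT [ALT], sodium, uric acid, phosphorus, magnesium", which helps in interpreting the QTc.

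**Report.** List QTcF by time since the last vorinostat dose where records allow; the diary collected under 9.1.7 may help. For earlier patients, state that the protocol did not require ECGs to be timed to vorinostat dosing.

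**Cost.** One footnote, one exemption, two time fields, and a wait before the infusion at one visit. No ECG or visit is added, an ECG before the second infusion is kept for myocarditis monitoring, and the C1D8 visit window is unchanged. C2D1 is no longer a pre-vorinostat ECG, and because it follows the first dose of a cycle it would not show an effect that builds over several dosing days. Moving the ECG to C1D8 would address that, but it gives up the ECG before the second infusion. It also conflicts with that visit's ±3-day window: days 5 to 11 include days 6 and 7, which are off drug at levels 1 and 2.
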